13.3 Ethics and Good Clinical Practice (GCP)	25
13.4 Study Documentation	26
13.5 Records Retention	26
13.6 Multi-center Guidelines	26
14: STATISTICAL CONSIDERATIONS	26
14.1 Study Design/Endpoints	27
14.2 Sample Size/Accrual Rate	27
14.3 Stratification Factors	27
14.4 Analysis of Secondary Endpoints	27
14.5 Reporting and Exclusions	28
15: PUBLICATION PLAN	28
16. REFERENCES	30
17: APPENDICES	30
Appendix 1	31
Performance Status Criteria	
Appendix 2	32
FACT-En Version 4 questionnaire for women with uterine cancer	
Appendix 3	35
FACT-Cx Version 4 questionnaire for women with cervical cancer	

Study Schema:

CONFIDENTIAL

This document is confidential. Do not disclose or use except as authorized.

1. OBJECTIVES:

The study hypotheses are that adjuvant post-hysterectomy proton teletherapy for women with uterine and cervical cancers and histologically confirmed metastases to regional lymph nodes will be efficacious (cancer control within the irradiated volume) and reduced in both acute and delayed toxicity when compared to treatment with conventional photon teletherapy techniques. The study will quantitate the magnitude of normal tissue spared with scanning proton beam therapy compared to 3-dimensional conformal and intensity modulated photon radiation techniques, and correlate acute and late toxicity outcomes to the reduced volumes of normal tissues irradiated.

1.1 Study Design:

Patients who undergo hysterectomy for invasive cancer of the uterus or cervix who have histologically confirmed metastases to one or more regional lymph nodes (parametrial, pelvic, or para-aortic nodal groups) conventionally undergo radiation treatment as all, or a component of their adjuvant post-surgical therapy.

Such patients will be identified at the weekly Gynecologic Oncology-Pathology Multidisciplinary Tumor Board that routinely reviews all gynecologic cancer pathology in patients operated at Massachusetts General Hospital (MGH).

Potentially eligible patients operated elsewhere and referred for adjuvant treatment to MGH would be identified based on pathology review of submitted histologic sections from the referring institution.

After obtaining informed consent, eligible patients will receive conventional doses of adjuvant teletherapy conventionally scheduled (fractionated) delivered to conventional target volumes using scanning proton beam instead of photon beam.

Using data from the same treatment planning CT scans used to plan proton therapy, conventional photon plans will be generated using three dimensional conformal radiation therapy (3DCRT) and intensity modulated radiation therapy (IMRT) for comparison purposes to quantitate the extent of normal tissue sparing through the use of dose volume histograms.

Monitoring during and after such treatment will be essentially equivalent to standard clinical practice at MGH with the exception that the schedule of post-treatment assessments will more tightly conform to the study calendar.

Assuming successful accrual and treatment of sufficient numbers of patients, a retrospective outcomes study will compare cancer control within the irradiated volume, acute side effects of teletherapy, and delayed complications of radiation treatment to a historical control population treated with photon teletherapy at MGH.

CONFIDENTIAL

This document is confidential. Do not disclose or use except as authorized.

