1.2 Primary Objective

1.2.1 In a population of women with cancers of the cervix or endometrium with pathologically proven spread to regional lymph nodes, to quantitate the magnitude of the normal tissue radiation dose reductions achieved by comparison of dose volume histograms achieved by scanning proton beam teletherapy with dose volume histograms of treatment plans for the same patients using 3-dimensional conformal radiation therapy (3DCRT) and intensity modulated radiation therapy (IMRT).

1.2.2 To prospectively assess acute radiation side effects and delayed complications in proton treated patients and to compare toxicity outcomes (acute side effects and delayed complications) with patients historically treated with photon teletherapy using institutional historical controls (retrospective outcomes comparison study).

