6. EXPECTED TOXICITIES AND DOSING DELAYS/DOSE MODIFICATIONS

Dose delays and modifications will be made using the following recommendations. Toxicity assessments will be done using NCI Common Terminology Criteria for Adverse Events (CTCAE v4.02 from 9/15/2009) which is available at <http://ctep.cancer.gov/reporting//ctc.html>.

All adverse events experienced by participants will be collected from the time of the first dose of study treatment, through the study and until the final study visit. Participants continuing to experience toxicity at the off study visit may be contacted for additional assessments until the toxicity has resolved or is deemed irreversible.

CONFIDENTIAL

This document is confidential. Do not disclose or use except as authorized.

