7. DRUG FORMULATION AND ADMINISTRATION: N/A

8. CORRELATIVE/SPECIAL STUDIES: N/A

9. STUDY CALENDAR

9.1 Baseline hematologic evaluations are to be conducted within 2-weeks prior to study entry. Scans must be done \leq 10 weeks prior to study entry.

9.2 Patients will be interviewed and examined weekly during treatment.

9.3 Routine surveillance follow-up will be: 3, 6, 9, 12, 15, 18, 21, 24, 28, 32, 36, 42, 48, 54 and 60 months (+/- 4 weeks) following adjuvant radiation treatment.

CONFIDENTIAL

This document is confidential. Do not disclose or use except as authorized.

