12.1.2 Data Submission

The schedule for completion and submission of case report forms (paper or electronic) to the ODQ is as follows:

Form	Submission Timeline
Eligibility Checklist	Complete prior to registration with ODQ
On Study Form	Within 14 days of registration
Baseline Assessment Form	Within 14 days of registration
Treatment Form	Within 10 days of the last day of the treatment
Toxicity Form	Weekly during treatment; within 14 days of protocol defined follow-up visit
Lab Form	With Baseline assessment form and weekly during treatment
Adverse Event Report Form	Immediately upon detection of adverse event

CONFIDENTIAL

This document is confidential. Do not disclose or use except as authorized.

	during treatment. Within 14 days of adverse event detected during surveillance follow-up.
Off Treatment/Off Study Form	Within 14 days of being taken off study for any reason
Follow up/Survival Form	Within 14 days of the protocol defined follow up visit date or call

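### The historical toxicity comparison sets prospectively graded proton events against retrospective photon records, and nothing in the plan separates modality from how events were found and graded

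*Combined protocol and SAP*

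**What the plan says.** The second part of the primary objective (Section 1.2.2) is "To prospectively assess acute radiation side effects and delayed complications in proton treated patients", and then to compare those outcomes with "patients historically treated with photon teletherapy using institutional historical controls (retrospective outcomes comparison study"). Section 1.1 repeats the plan for acute and delayed effects, with the proton outcomes compared "to a historical control population treated with photon teletherapy at MGH", subject to adequate accrual.

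For proton patients the collection is laid out in detail:

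- Section 9.2: "Patients will be interviewed and examined weekly during treatment".
- Section 12.1.2, timing of the toxicity form: "Weekly during treatment; within 14 days of protocol defined follow-up visit".
- Section 6: "Toxicity assessments will be done using NCI Common Terminology Criteria for Adverse Events", version 4.02.
- Section 9.3: "Routine surveillance follow-up will be: 3, 6, 9, 12, 15, 18, 21, 24, 28, 32, 36, 42, 48, 54 and 60 months", each within 4 weeks.

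For photon controls the documents state only the institution and the retrospective design. They do not give the number of patients, treatment era, eligibility, grading scale, time windows or method of abstraction. Section 14 says that toxicity rates will be determined and that GI toxicity will be a major focus, but sets out no analysis for the photon comparison.

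One sentence in Section 1.1 bears on the other side. It says that monitoring on the study will be close to the institution's usual practice, except that post-treatment assessments will follow the study calendar more strictly.

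**The concern.** All proton events enter through one system of ascertainment and all photon events through another. Modality and ascertainment are therefore completely aliased: no patient treated with one modality is assessed in the other's way, and the plan names no analysis that could separate the two effects.

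This matters most for symptoms whose recording depends on being asked and graded, such as cramps, urgency, diarrhoea and fatigue. These make up most of the acute effects that Section 6.1 rates as likely. If retrospective review misses photon events, a real proton benefit shrinks, disappears or reverses. If staff who know the treatment grade proton patients leniently, a benefit can appear where none exists. Section 1 hypothesises reduced acute and delayed toxicity against photons, so the comparison bears on a stated aim.

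**Working it through.** **The plan's own figures.** The only operating characteristics given are for the dose-volume endpoint (Section 14.1): at least 20 successes in 22 patients. The exact binomial tail gives

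- P(X ≥ 20 | n = 22, p = 0.95) = 0.905, against the stated 91%;
- P(X ≥ 20 | n = 22, p = 0.80) = 0.154, against the stated 15%.

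Both reproduce, but neither bears on toxicity. No figure is given for the toxicity comparison.

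**Ascertainment side by side.**

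| | Proton | Photon controls |
|---|---|---|
| Collection | Prospective (1.2.2) | Retrospective (1.1, 1.2.2) |
| Grading | CTCAE v4.02 (6, 11.1) | Not stated |
| On-treatment recording | Weekly toxicity form (12.1.2) | Not stated; visits possibly similar (1.1) |
| Post-treatment schedule | 15 fixed visits to 60 months (9.3) | Usual practice, less tightly scheduled (1.1) |
| Imaging | CT twice a year to year 3 (9.4) | Not stated |

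Weekly assessment applies only on treatment. Late effects are collected at visits 3 to 6 months apart, still prospectively.

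**Illustration of size.** The documents give neither rates nor capture shares, so every input here is an assumption. Let the apparent photon rate be the true rate × s, where s is the share of photon events found by retrospective review, and assume full capture for protons.

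*True rates 50% photon and 35% proton (a 15-point benefit):*

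- s = 0.8: 0.50 × 0.8 = 0.40; 0.35 − 0.40 = −0.05, so protons look 5 points better.
- s = 0.7: 0.50 × 0.7 = 0.35; the difference is 0.
- s = 0.6: 0.50 × 0.6 = 0.30; 0.35 − 0.30 = +0.05, so protons look 5 points worse.

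*No true difference, both 50%:*

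- s = 0.8: 0.50 − 0.40 = 0.10, so protons look 10 points worse.
- s = 0.6: 0.50 − 0.30 = 0.20, so protons look 20 points worse.

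*The opposite direction:* with both true rates at 50%, full photon capture and an assumed 90% of proton events scored, 0.50 × 0.9 = 0.45, a spurious 5-point benefit.

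**Precision with 22 patients.** An observed 8/22 (36%) has an exact 95% interval of about 17% to 59%. For a true 50% against 30% with full capture on both sides, power at two-sided 0.05 is about 27% with an assumed 22 controls and 33% with 44. At 80% photon capture these fall to about 10% and 12%.

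**Are harder events neutral?** Not automatically.

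- Treatment suspension and IV hydration follow protocol triggers in Sections 6.1.2 and 6.2. The rules that applied to photon patients are not stated. Section 5.2.3 also foresees proton beam downtime, which has nothing to do with toxicity.
- Transfusion is discretionary (5.4.1).
- Scheduled CT could detect more fractures in the proton cohort.
- Surgery for bowel obstruction depends little on grading but is rare. At the 1% to 10% of Section 6.1, 22 × 0.01 to 22 × 0.10 gives 0.2 to 2.2 expected events. With about 14 uterine and 8 cervical patients this is 0.1 to 1.4 and 0.1 to 0.8.

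**The case against.** The best defence is the Section 1.1 sentence on monitoring. If study monitoring is close to usual practice, photon patients may also have been seen weekly on treatment, and the acute-phase difference would lie in grading and recording rather than in visits. That stands. A reader might infer that photon patients were scarcely monitored, or that their low-grade symptoms were recorded far less often. The documents are silent on photon-era recording and support neither statement. But the sentence does not say how toxicity was graded or recorded in past patients, and it exempts the post-treatment schedule, which governs delayed complications.

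A second defence is that no decision rests on the comparison. Section 14.1 makes the dose-volume comparison the primary endpoint, no test or margin is attached to toxicity against photons, and the comparison is conditional on accrual. This limits the consequence, but Section 1.2.2 still lists the comparison under Primary Objective and no other document is named as holding its rules.

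Third, with 22 patients the comparison would be imprecise even if ascertainment were perfect. That is also true. Imprecision shows in a confidence interval, however, while ascertainment bias does not.

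**Conclusion.** The concern holds as a gap in the plan. A listed primary objective compares cohorts with different ascertainment, and no planned analysis separates that from modality. The documents do not give the size of the bias. Under the stated assumptions (50% against 35%, full proton capture, 60% to 80% photon capture) a 15-point benefit would appear as anything from 5 points worse to 5 points better.

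A reader might infer that the bias must hide a proton benefit, or that it defeats the trial's hypothesis. Neither follows. The direction is unknown, because unblinded prospective grading could favour protons, and the powered endpoint is dosimetric and untouched. Nor does it follow that symptoms must be dropped from the comparison altogether, since that would remove most of its acute part. They need common ascertainment and a descriptive label.

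**What to change.** In Sections 1.1 and 1.2.2, state that the historical comparison uses only outcomes ascertained the same way in both cohorts: routine records as the source for proton and photon patients alike, one abstraction form, one CTCAE version and the same time windows. Present results within tumour site or adjusted for it, since Section 5.2.20 places chemotherapy before radiation in uterine cancer and allows it concurrently in cervical cancer.

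Give most weight to events that depend least on grading, such as hospital admission and surgery for bowel obstruction, while acknowledging how few are expected. Do not treat treatment interruption, IV hydration, transfusion or imaging-detected fracture as neutral unless triggers and imaging schedules are shown to be comparable.

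Report the prospective form-based rates, including low-grade symptoms, as proton-only estimates with intervals. Label any symptom comparison with photon controls descriptive and note the wide uncertainty with 22 patients.

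The cost is some chart abstraction, for both cohorts, within the retrospective study already planned, and weaker claims on symptomatic endpoints. Proton patients need no extra assessments.

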1.2 Primary Objective

1.2.1 In a population of women with cancers of the cervix or endometrium with pathologically proven spread to regional lymph nodes, to quantitate the magnitude of the normal tissue radiation dose reductions achieved by comparison of dose volume histograms achieved by scanning proton beam teletherapy with dose volume histograms of treatment plans for the same patients using 3-dimensional conformal radiation therapy (3DCRT) and intensity modulated radiation therapy (IMRT).

1.2.2 To prospectively assess acute radiation side effects and delayed complications in proton treated patients and to compare toxicity outcomes (acute side effects and delayed complications) with patients historically treated with photon teletherapy using institutional historical controls (retrospective outcomes comparison study).

1.3 Secondary Objectives

1.3.1 To prospectively collect data on quality of life (QOL) before and after adjuvant scanning proton beam therapy employing contemporary, validated instruments tailored for women treated for gynecologic cancer.

1.3.2 To determine the progression-free survival and patterns of recurrence with this treatment.

2. BACKGROUND

2.1 Study Agent(s)

2.1.1 Proton beam radiation therapy has been employed in the clinical treatment of cancer at MGH since 1961. Initially patients were treated at the Harvard Cyclotron Laboratory in Cambridge, but since 2001 treatment has been administered on the MGH campus in the Francis H. Burr Proton Treatment Center. To date, over 10,000 patients have been treated using proton beam in MGH programs. Proton beam has equivalent biologic effects in tissue to high energy photon beams from linear accelerators employed at MGH and elsewhere. The principal clinical advantage of proton beam lies in the nature of its energy (radiation dose) deposition in tissue. In contrast to photons (X-rays), protons penetrate to a depth in tissue determined by their energy, then deposit dose over a very narrow range (Bragg peak) transmitting minimal radiation beyond that point. Exploiting this difference in physical dose deposition characteristics allows design of clinical treatments with more conformal dose distributions delivering proportionately much lower dose to normal tissues lying adjacent to the targeted malignant tissues than conventional photon techniques. [1] In general, this will result in milder acute treatment side effects, and potentially fewer and milder long-term complications of radiation treatment.

CONFIDENTIAL

This document is confidential. Do not disclose or use except as authorized.

2.2 Study Disease:

2.2.1 Patients with primary cancers of the uterus conventionally undergo surgery as their initial intervention. Generally this will consist of open or laparoscopic total hysterectomy and bilateral salpingo-oophorectomy with variable sampling or full dissection of pelvic and/or para-aortic lymph nodes. Patients in whom cancer has spread to lymph nodes (International Federation of Gynecology and Obstetrics (FIGO) Stage IIIC) routinely undergo radiation treatment to the pelvis or extended volumes (pelvis and para-aortic nodal basins) postoperatively, either as their only adjuvant treatment, or more commonly following 4-6 cycles of adjuvant systemic cytotoxic chemotherapy with carboplatin and taxol. Such treatment is endorsed by National Comprehensive Cancer Network (NCCN) guidelines.[2] Teletherapy (external radiation) is commonly supplemented by limited additional vaginal brachytherapy (internal vaginal radiation). This approach has been standard management at MGH for more than 7 years and is also endorsed by National Comprehensive Cancer Network (NCCN) guidelines.[2] Based on retrospective outcomes comparisons from M.D. Anderson Cancer Center, cancer control and overall survival statistics are substantially better in patients getting teletherapy/brachytherapy as all or a component of their treatment compared to patients getting systemic adjuvant chemotherapy/brachytherapy without teletherapy.[3] Additional data from Duke University and the University of North Carolina support this approach as well.[4]

2.2.2 Patients with primary cancer of the cervix limited to the cervix and upper vagina (FIGO stages IB and IIA) based on examination under anesthesia (EUA) supplemented by diagnostic imaging (MRI, PET/CT) will conventionally undergo modified radical or radical hysterectomy with therapeutic pelvic lymphadenectomy +/- sampling para-aortic lymphadenectomy as their initial therapeutic intervention. Patients with histologically confirmed metastasis to lymph nodes undergo adjuvant teletherapy to the pelvis or extended volumes (pelvis and para-aortic nodal basins) administered in conjunction with concurrent cisplatin-based adjuvant cytotoxic chemotherapy and limited intra-vaginal brachytherapy. This has been standard therapy at MGH for more than 7 years and is consistent with NCCN guidelines.[2]

2.3 Rationale

While combined modality therapy (surgery, radiotherapy, chemotherapy) for patients with FIGO Stage IIIC uterine cancer and American Joint Commission on Cancer (AJCC) pT_{1,2},N₁,M₀ cancer of the cervix is associated with prolonged cancer-free survival (“cure”) in many patients [3,4,5] acute side effects and late complications of treatment can be severe with substantial impact on quality of life (QOL) for many subsequent years. Despite chronic toxicities of treatment being recognized by both patients and the physicians involved in their longitudinal care, minimal prospective data are available documenting the impact of such treatment on quality of life, and no

CONFIDENTIAL

This document is confidential. Do not disclose or use except as authorized.

quantitative data employing contemporary assessment instruments tailored for women with gynecologic malignancies.

Acute toxicities associated with radiation treatment include cramps, erratic bowel movements, diarrhea, nausea, vomiting, dehydration, electrolyte imbalance, urinary frequency, burning, and fatigue.

Late complications, which occur months to years after radiation treatment, can include leg lymphedema, radiation insufficiency fractures in pelvic bones or lumbar spine, small or large bowel obstruction which can require surgery to relieve, or chronic erratic bowel function with varying degrees of intestinal malabsorption. In some premenopausal patients with cervical cancer, ovaries will be conserved, often surgically translocated to the para-colic gutters. Teletherapy is often a contributing factor in the premature endocrine failure of such ovaries, resulting in premature menopause.

Both acute side effects and late complications of radiation treatment are mostly a function of the volume of adjacent organs at risk (OAR), the “innocent bystanders” that are unavoidably irradiated when conventional photon beam techniques are employed to target potentially cancerous tissues. Volume of normal tissue exposed, total dose, and dose per treatment fraction all correlate with the severity of both acute symptomatic side effects as well as late effects in normal tissues. Each of these parameters could be expected to be reduced by using proton beam therapy [1] rather than conventional photon beam techniques, with resultant better tolerance during treatment as well as reduced late complications. Virtually every patient undergoing pelvic or extended volume teletherapy will experience some degree of acute side effects. Only a minority will experience major symptomatic late complications. But for those patients, the effects can last a lifetime.

The hypothesis of this study is that use of proton beam teletherapy in-lieu of conventional photon techniques will result in reduced radiation exposure to normal tissues and reduced side effects and complications of treatment. Use specifically of the “pencil-beam” scanning (PBS) proton capability at the FHBPTC makes the treatment of these protocol patients practically feasible by reducing the complexity of treatment planning and delivery compared to scattered proton fields. Due to limitations on field size and deep range of scattered proton fields, treatment of large, deep-seated target volumes becomes complex, time consuming, and expensive. PBS reduces costs incurred in the construction of field-specific hardware and provides more conformal dose distributions.[6,7]

